8.6.1.2 Overall Survival

The non-parametric Kaplan-Meier method will be used to estimate the survival curves in each treatment group including the OS rates at 12, 18, and 24 months (based on data adequacy). The treatment difference in survival will be assessed by the stratified log-rank test. A stratified Cox proportional hazard model with Efron's method of tie handling will be used to assess the magnitude of the treatment difference (i.e., the hazard ratio). The hazard ratio and its 95% CI from the stratified Cox model with a single treatment covariate will be reported. The stratification factors used for randomization (See Section 5.4) will be applied to both the stratified log-rank test and the stratified Cox model.

8.6.1.3 Objective Response Rate

Stratified Miettinen and Nurminen’s method with weights proportional to the stratum size will be used for comparison of the objective response rates between the treatment arms. A 95% CI for the difference in response rates between the treatment arms will be provided. The stratification factors used for randomization will be applied to the analysis. Sensitivity analyses will be performed to assess ORR based on investigator's assessment.

The ORR analysis will be conducted according to the hypothesis testing plan as described in Section 8.7 – Interim Analyses and Section 8.8 – Multiplicity.

8.6.1.4 Duration of Response

The non-parametric Kaplan-Meier method will be used to estimate the DOR curve in each treatment group; estimates of the percentage of subjects still in response and 95% CIs at specific duration time points will be provided.

Sensitivity analyses will be performed to assess DOR based on investigator's assessment.

For each DOR analysis, a corresponding summary of the reasons responding subjects are censored will also be provided.

Censoring rules for DOR are summarized in [Table 17](#).

Table 17 Censoring Rules for DOR

Situation	Date of Progression or Censoring	Outcome
No progression nor death, no new anti-cancer therapy initiated	Last adequate disease assessment	Censor (Non-event)
No progression nor death, new anti-cancer therapy initiated	Last adequate disease assessment before new anti-cancer therapy initiated	Censor (Non-event)
Death or progression immediately after ≥ 2 consecutive missed disease assessments or after new anti-cancer therapy, if any	Earlier date of last adequate disease assessment prior to ≥ 2 missed adequate disease assessments and new anti-cancer therapy, if any	Censor (Non-event)
Death or progression after ≤ 1 missed disease assessments and before new anti-cancer therapy, if any	PD or death	End of response (Event)
A missed disease assessment includes any assessment that is not obtained or is considered inadequate for evaluation of response. Subjects are considered to have an ongoing response if censored, alive, have not progressed, have not started a new anti-cancer therapy and have not been determined to be lost to follow-up. Abbreviations: DOR=duration of response; PD=progressive disease.		

8.6.1.5 Disease Control Rate

Stratified Miettinen and Nurminen’s method with weights proportional to the stratum size will be used for comparison of the DCR between the treatment arms. A 95% CI for the difference in response rates between the treatment arms will be provided. The stratification factors used for randomization will be applied to the analysis. Sensitivity analyses will be performed to assess DCR based on investigator's assessment.

8.6.1.6 Summary of Statistical Methods for Efficacy

Table 18 summarizes the primary analysis approach for primary and secondary efficacy endpoints. Sensitivity analysis methods are described above for each endpoint.

The strategy to address multiplicity issues with regard to multiple efficacy endpoints, multiple populations, and interim analyses is described in Section 8.7 Interim Analyses and in Section 8.8 Multiplicity.

Table 18 Analysis Strategy for Key Efficacy Endpoints

Endpoint/Variable (Description, Time Point)	Statistical Method [†]	Analysis Population	Missing Data/ Censoring Approach
Primary Hypothesis #1			
PFS per RECIST 1.1 by BICR	Test: Stratified Log-rank test Estimation: Stratified Cox model with Efron's tie handling method	ITT	
 • Primary censoring rule • Sensitivity analysis 1 • Sensitivity analysis 2
Primary Hypothesis #2			
OS	Test: Stratified Log-rank test Estimation: Stratified Cox model with Efron's tie handling method	ITT	Censored at the last date the subject was known to be alive
Secondary Hypothesis			
ORR per RECIST 1.1 by BICR	Stratified M & N method [‡]	ITT	Subjects with missing data are considered non-responders

[†] Statistical models are described in further detail in the text. For stratified analyses, the stratification factors used for randomization (see Section 5.4) will be applied to the analysis model.

[‡] Miettinen and Nurminen method.

Abbreviations: BICR=blinded independent central imaging review; ITT=intention-to-treat; ORR=objective response rate; OS=overall survival; PFS=progression-free survival

8.6.2 Statistical Methods for Safety Analyses

Safety and tolerability will be assessed by clinical review of all relevant parameters including AEs, laboratory tests, and vital signs.

Tiered Approach

The analysis of safety results will follow a tiered approach (Table 19). The tiers differ with respect to the analyses that will be performed. For this protocol, there are no Tier 1 events.

Tier 2 parameters will be assessed via point estimates with 95% CIs provided for between-group comparisons; only point estimates by treatment group are provided for Tier 3 safety parameters.

Adverse events (specific terms as well as system organ class terms) will be classified as belonging to "Tier 2" or "Tier 3", based on the number of events observed. Membership in Tier 2 requires that at least 10% of the subjects in any treatment group exhibit the event; all other AEs and predefined limits of change will belong to Tier 3.

The threshold of at least 10% of subjects with events was chosen for Tier 2 event because the incidence rate would allow meaningful statistical assessments; events reported in less frequent than 10% of subjects would obscure the assessment of overall safety profile and add little to the meaningful interpretation. Because many 95% CIs may be provided without adjustment for multiplicity, the confidence intervals should be regarded as a helpful descriptive measure to be used in review, not a formal method for assessing the statistical significance of the between-group differences in AEs and predefined limits of change.

Continuous measures such as changes from baseline in laboratory values and vital signs that are not pre-specified as Tier 1 safety parameters will be considered Tier 3 safety parameters. Summary statistics for baseline, on-treatment, and change from baseline values will be provided by treatment group in table format.

In addition, the broad clinical and laboratory AE categories consisting of the percentage of subjects with Grade 3-5 AE (incidence $\geq 5\%$ of subjects in one of the treatment groups) and any SAE (incidence $\geq 5\%$ of subjects in one of the treatment groups) will be considered Tier 2 endpoints.

The threshold of at least 5% of subjects with events was chosen for Tier 2 Grade 3-5 AEs and SAEs because the incidence rate would allow meaningful statistical assessments; those AEs are expected to happen less frequent than specific AEs/SOCs but important for overall safety profile assessment.

The broad clinical and laboratory AE categories consisting of the percentage of subjects with any AE, any Grade 3-5 AE (incidence $< 5\%$ of subjects in one of the treatment groups), any SAE (incidence $< 5\%$ of subjects in one of the treatment groups), any drug-related AE, any AE that is both drug-related and Grade 3-5, any AE that is both serious and drug related, dose modification due to AE, discontinuation due to an AE, and death will be considered Tier 3 endpoints.

Note that 95% CIs will be provided for between- treatment differences in the percentage of subjects with Tier 2 events; these analyses will be performed using the Miettinen and Nurminen method, an unconditional, asymptotic method.

Table 19 Analysis Strategy for Safety Parameters

Safety Tier	Safety Endpoint	95% CI for Treatment Comparison	Descriptive Statistics
Tier 2	Any Serious AE (incidence $\geq 5\%$ of subjects in one of the treatment groups)	X	X
	Any Grade 3-5 AE (incidence $\geq 5\%$ of subjects in one of the treatment groups)	X	X
	Specific AEs or SOCs (incidence $\geq 10\%$ of subjects in one of the treatment groups)	X	X
Tier 3	Any AE		X
	Any Serious AE (incidence $< 5\%$ of subjects in one of the treatment groups)		X
	Any Grade 3-5 AE (incidence $< 5\%$ of subjects in one of the treatment groups)		X
	Any Serious and Drug-related AE		X
	Any Grade 3-5 and Drug-related AE		X
	Dose Modification due to AE		X
	Discontinuation due to AE		X
	Death		X
	Specific AEs or SOCs (incidence $< 10\%$ of subjects in all of the treatment groups) or PDLCs		X
	Change from Baseline Results (Labs, ECGs, Vital Signs)		X

Abbreviations: AE = adverse event; CI = confidence interval; ECG = electrocardiogram; PDLC = pre-defined limit of change; SOC = system organ class.

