3.2 Secondary Objective(s) & Hypothesis(es)

- (1) **Objective:** To compare ORR and DCR per RECIST 1.1 as assessed by BICR in subjects treated with a combination of pembrolizumab plus axitinib versus sunitinib monotherapy. DOR will also be evaluated.

Hypothesis: The combination therapy of pembrolizumab plus axitinib is superior to sunitinib monotherapy with respect to ORR as assessed by BICR per RECIST 1.1.

- (2) **Objective:** To evaluate PFS rate per RECIST 1.1 as assessed by BICR at 12, 18, and 24 months based on data adequacy; to evaluate OS rates at 12, 18, and 24 months based on data adequacy.
- (3) **Objective:** To evaluate and compare safety and tolerability profiles in subjects treated with pembrolizumab plus axitinib versus sunitinib monotherapy.
- (4) **Objective:** To compare time to deterioration (TTD) based on the Functional Assessment of Cancer Therapy Kidney Symptom Index—Disease-Related Symptoms (FKSI-DRS) scale in subjects treated with pembrolizumab plus axitinib versus sunitinib monotherapy.
- (5) **Objective:** To assess the longitudinal score changes from baseline to 42 weeks as measured by European Organization for the Research and Treatment of Cancer (EORTC) QLQ-C30 global health status/quality of life scale.

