Based on the known toxicity profiles of pembrolizumab and axitinib, certain treatment-related AEs are uniquely associated with one drug versus the other. For example, hypertension, arterial thrombotic events, proteinuria, and hemorrhagic events are known risks for axitinib treatment, while immune-related AEs are risks for pembrolizumab treatment. However, certain AEs may be initially considered attributed to either study drugs, such as diarrhea, hypothyroidism, and liver enzyme elevation. Therefore, evaluation of attribution is important for determining the study drug most likely related to the AE, or an alternative etiology, and subsequently proper clinical management. The following aspects should be considered:

1. Timing of AE onset:

Since axitinib is dosed BID continuously due to a short half-life, and pembrolizumab is dosed Q3W due to a long half-life, axitinib can be interrupted to assess whether an AE improves/resolves with dechallenge (i.e., interruption of treatment) based on the following two scenarios.

- If an AE occurs during a treatment cycle (i.e., between 2 pembrolizumab doses), only axitinib dose interruption is needed.
- If an AE occurs at the beginning of a treatment cycle, axitinib can be interrupted and dosing of pembrolizumab should be held.

If a subject recovers from an AE in response to axitinib interruption (i.e., positive dechallenge), the event is more likely to be attributed to axitinib. Otherwise, after excluding other alternative explanations, an immune-related AE should be considered.

2. Severity of AE:

If an AE is suspected to be treatment related and is severe/life threatening at the time of onset or is rapidly worsened, action including interrupting or holding both drugs and initiating treatment with a corticosteroid (with exception of hypothyroidism, T1DM) and other supportive care should be taken promptly.

5.2.2.3.1 Evaluation and management of ALT/AST elevations during axitinib and pembrolizumab combination therapy

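### Low-incidence immune-related AEs get no planned treatment difference or CI, because Section 8.6.2 selects AE terms by frequency alone and defines no immune-related category

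*Combined protocol and SAP*

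**What the plan says.** Section 8.6.2 sorts safety results into tiers, and the tier decides what is reported.

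- **Tier 1:** empty. "For this protocol, there are no Tier 1 events".
- **Tier 2:** a difference between arms with a Miettinen-Nurminen 95% CI. The rule for terms and organ classes is "Membership in Tier 2 requires that at least 10% of the subjects in any treatment group exhibit the event". For the more severe events, "The threshold of at least 5% of subjects with events was chosen for Tier 2 Grade 3-5 AEs and SAEs".
- **Tier 3:** everything else, where "only point estimates by treatment group are provided for Tier 3 safety parameters".

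The reason given for the 10% cut-off is that "events reported in less frequent than 10% of subjects would obscure the assessment of overall safety profile and add little to the meaningful interpretation". The rule works at two levels of coding: "Adverse events (specific terms as well as system organ class terms) will be classified as belonging to" Tier 2 or Tier 3. No level in between is defined. Neither Section 8.6.2, Table 19 nor the safety endpoints in Section 4.2.3.2 contains an immune-related AE category, and Section 8.6.2 does not leave one to the supplemental SAP. The events of clinical interest in Section 7.2.3.2 cover overdose and liver tests only.

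Elsewhere the protocol treats these events as a class. Section 5.2.2.3 sets axitinib's known risks beside pembrolizumab's: "while immune-related AEs are risks for pembrolizumab treatment". Table 6 manages them by named category. Secondary objective 3 in Section 3.2 is comparative: "To evaluate and compare safety and tolerability profiles in subjects treated with pembrolizumab plus axitinib versus sunitinib monotherapy".

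**The concern.** The protocol manages immune-related AEs by category but does not analyse them by category. Whether one of them gets a treatment difference depends on how often its single term happens to be reported. Table 6 calls for permanent discontinuation of pembrolizumab for several of them, including Grade 3 or 4 pneumonitis, nephritis and myocarditis and Grade 4 colitis, so they matter even when infrequent.

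Two things are at stake. First, an informative difference in an infrequent event would not be among the planned outputs. Second, if a category is coded under several terms, the number of subjects affected cannot be rebuilt from the term tables, because one subject may have more than one term. Any grouping made after the data are seen, in an open-label trial, is open to the charge of selective grouping.

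**Working it through.** The plan gives no computed figure here; the cut-offs are rules, so there is nothing to reproduce. The check has three parts: which events the rule excludes, which it admits, and whether the excluded ones really add little.

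**Inputs**
- 861 subjects randomized 1:1 (Sections 8.9 and 5.3). 861/2 = 430.5, taken as n = 430 per arm. This assumes that nearly all randomized subjects are treated and so enter the ASaT population.
- Cut-offs of 10% and 5% (Section 8.6.2, Table 19).
- Immune-mediated hepatitis of 0.7% any grade and 0.4% Grade 3 among 2799 subjects on pembrolizumab monotherapy (Section 5.2.2.3.1).
- Term rates in the 52-subject combination study (Table 2).

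**1. What is excluded.** The cut-offs in subjects are 0.10 × 430 = 43 and 0.05 × 430 = 21.5, so 22. With X ~ Binomial(430, p), the chance that one arm reaches them is:

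| True incidence p | P(X ≥ 43), any-grade term | P(X ≥ 22), SAE or Grade 3-5 |
|---|---|---|
| 0.7% | 5 × 10⁻³⁵ | 1 × 10⁻¹² |
| 3% | 1 × 10⁻¹¹ | 0.012 |
| 5% | 2 × 10⁻⁵ | 0.49 |
| 8% | 0.08 | 0.99 |

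Any term with a true any-grade rate of about 5% or less is therefore almost certain to stay in Tier 3. The 5% rule brings in a serious or Grade 3-5 event only if that event itself runs near 5% or more.

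**2. What is admitted.** Table 6 also lists diarrhea/colitis, hypothyroidism and AST/ALT elevation. Table 2 reports diarrhea in 37/52 (71.2%), hypothyroidism in 19/52 (36.5%), ALT increased in 18/52 (34.6%) and AST increased in 16/52 (30.8%). The lower Clopper-Pearson 95% limits are 56.9%, 23.6%, 22.0% and 18.7%. Even at those limits the chance of reaching 43 of 430 is above 0.999. These events will be compared, but as all-cause terms. Section 5.2.2.3 itself says that diarrhea, hypothyroidism and liver enzyme elevation may come from either drug.

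**3. Whether events below the cut-off add little.** The Miettinen-Nurminen limits are the values δ that solve

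(d − δ) / √{[p̃₁(1−p̃₁)/n + p̃₂(1−p̃₂)/n] × 2n/(2n−1)} = ±1.96,

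where d is the observed difference and p̃₁, p̃₂ are the maximum-likelihood rates under p₁ − p₂ = δ. With n = 430 and assumed counts:

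| Combination vs sunitinib | Difference (points) | 95% CI |
|---|---|---|
| 17 vs 4 | (17−4)/430 = 3.0 | 1.1 to 5.4 |
| 13 vs 2 | (13−2)/430 = 2.6 | 0.9 to 4.7 |
| 6 vs 0 | 6/430 = 1.4 | 0.5 to 3.0 |
| 3 vs 0 | 3/430 = 0.7 | −0.2 to 2.0 |

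All four rows are below both cut-offs. The first three exclude zero. The last matches the one documented rate (0.007 × 430 ≈ 3) and is inconclusive.

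**The case against.** The case for leaving the rule alone has real parts.

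- **Tier 2 CIs are descriptive.** Section 8.6.2 says so, and Tier 3 events are still reported by arm, so the difference for a single term is a subtraction. This stands. It makes the point one of reporting, and it sets the priority. It does not supply the interval, and it does not help a category spread over several terms.
- **Other safeguards exist.** Section 8.6.2 provides for clinical review of all relevant safety parameters, the DMC reviews safety every 4 months in the first year (Section 8.7), and hepatic events of clinical interest are reported within 24 hours (Section 7.2.3.2). This also stands, but none of it is a planned between-arm estimate.
- **The 5% rule catches some severe events.** True where a Grade 3-5 or serious event is near 5% or above. For example, 4 of 52 combination subjects (7.7%) had Grade 3 treatment-related liver events (Section 5.2.2.3.1); counted as one category, that rate reaches 22 of 430 with probability 0.99.
- **The illustrative counts are assumed.** Correct. They show that intervals below the cut-off can be informative, not that these differences will occur.
- **A pooled immune-related row would be swamped.** Diarrhea, thyroid and liver-enzyme terms would dominate it, and sunitinib's Table 11 lists these too. This stands and shapes the fix.

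A reader might infer more than the documents support. They do not show that immune-related AEs as a whole escape comparison, since the common ones in Table 6 enter Tier 2. They do not rank these events as the main added risk of the combination; Section 5.2.2.3 lists axitinib's own risks beside them. They do not map terms to organ classes, so nothing can be said from them about how far an organ-class row would dilute or rescue a given event.

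**Conclusion.** The point holds in a narrow form. Low-incidence immune-related events, such as pneumonitis, colitis, hypophysitis, nephritis, myocarditis, type 1 diabetes and immune-mediated hepatitis, would get term-by-term arm percentages and no planned difference or CI, and no immune-related category is pre-specified. The stated justification for the 10% cut-off does not hold at this sample size: excluded differences of about 1.4 to 3.0 points can have intervals clear of zero.

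This rests on two assumptions. The first is about 430 treated subjects per arm. The second is that the named events are infrequent, for which the documents give a figure only for immune-mediated hepatitis (0.7%, monotherapy). At that rate the added interval would itself be inconclusive.

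Type I error and the efficacy conclusions are not affected. The gap concerns how a comparative safety objective is estimated and reported. Priority: consider.

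**What to change.** In Section 8.6.2 and Table 19:

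1. Make each named Table 6 category Tier 2 whatever its incidence, for any grade and for Grade 3-5, with the Miettinen-Nurminen 95% CI already specified. Leave out the table's open-ended last row for other immune-related events, which cannot be a fixed list.
2. Define each category by a term list fixed before the first interim analysis, and count each subject once per category.
3. If a pooled row over the listed categories is added, show it also without diarrhea, thyroid and liver-enzyme terms, because these also occur with the VEGFR inhibitors.
4. Keep the 10% and 5% rules for everything else.

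The cost is SAP wording, the term lists and about 20 rows: nine named categories × 2 grade groupings = 18, plus any pooled rows. No new data and no alpha are needed. The downside is more unadjusted CIs, which Section 8.6.2 already labels descriptive.

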Based on the existing data from clinical trials, ALT/AST elevations have been observed in advanced cancer patients who received axitinib or pembrolizumab monotherapy treatment. In the Phase 3 study that compared axitinib versus sorafenib in treatment-naïve advanced RCC patients [15], laboratory data showed that the rate of ALT elevation was 40.4% for all grade, 29.8% for Grade 1, 6.7% for Grade 2, 3.9% for Grade 3, and zero for Grade 4. The AE data showed that reported ALT elevation regardless of causality was 10.6% for all grade, 4.8% for Grade 1, 2.6% for Grade 2, 3.2% for Grade 3, and zero for Grade 4. Similar results were observed for AST [unpublished data provided by Pfizer].

Based on data from 2799 subjects with either advanced melanoma or NSCLC treated with pembrolizumab monotherapy, the incidence of immune-mediated hepatitis was 0.7% for all grade, 0.4% for Grade 3, and no Grade 4 or 5 events [Pembrolizumab IB]. In the updated data from an ongoing Phase 1/2 study of axitinib plus pembrolizumab in treatment-naïve advanced RCC, 4 out of 52 subjects had Grade 3 and another 4 had Grade 2 treatment-related ALT/AST elevations or hepatic dysfunction.

Differentiation of whether ALT/AST elevations are attributable to axitinib or pembrolizumab or both may be challenging, as no specific clinical picture or laboratory markers are available. In addition, alternative causes (e.g., viral hepatitis and other severe infections, liver metastasis, ischemia, alcohol intake, etc.) should be excluded before more definitively concluding the attribution of ALT/AST elevation by the study drugs.

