7.2.3.2 Events of Clinical Interest

Selected non-serious and serious adverse events are also known as Events of Clinical Interest (ECI) and must be reported to the Sponsor.

For the time period beginning when the consent form is signed until treatment allocation/randomization, any ECI, or follow up to an ECI, that occurs to any subject must be reported within 24 hours to the Sponsor if it causes the subject to be excluded from the trial, or is the result of a protocol-specified intervention, including but not limited to washout or discontinuation of usual therapy, diet, placebo treatment or a procedure.

For the time period beginning at treatment allocation/randomization through 30 days following cessation of treatment, any ECI, or follow up to an ECI, whether or not related to the Sponsor's product, must be reported within 24 hours to the Sponsor, either by electronic media or paper. Electronic reporting procedures can be found in the EDC data entry guidelines. Paper reporting procedures can be found in the Investigator Trial File Binder (or equivalent).

Events of clinical interest for this trial include:

1. an overdose of Sponsor's product, as defined in Section 7.2.1 - Definition of an Overdose for This Protocol and Reporting of Overdose to the Sponsor, that is not associated with clinical symptoms or abnormal laboratory results.

2. an elevated AST or ALT lab value that is greater than or equal to 3X the upper limit of normal and an elevated total bilirubin lab value that is greater than or equal to 2X the upper limit of normal and, at the same time, an alkaline phosphatase lab value that is less than 2X the upper limit of normal, as determined by way of protocol-specified laboratory testing or unscheduled laboratory testing.*

*Note: These criteria are based upon available regulatory guidance documents. The purpose of the criteria is to specify a threshold of abnormal hepatic tests that may require an additional evaluation for an underlying etiology. The trial site guidance for assessment and follow up of these criteria can be found in the Investigator Trial File Binder (or equivalent).

3. The following events should also be reported as an ECI if they occur after the start of treatment in the axitinib/ pembrolizumab combination arm:
 - a. events with ALT and/or AST > 5xULN
 - b. events with ALT and/or AST > 3xULN concurrently with total bilirubin $\geq 2xULN$

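### The only between-arm liver estimates with a confidence interval rest on investigator-reported AE terms, although ALT, AST and bilirubin are measured on schedule in both arms

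*Combined protocol and SAP*

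**What the plan says.** Section 8.6.2 has no Tier 1 events. Only Tier 2 receives a between-group estimate with a 95% interval (Miettinen and Nurminen). Tier 2 holds specific AE terms or system organ classes reached by at least 10% of an arm, and Grade 3-5 AEs and SAEs reached by at least 5%.

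For laboratory data the section states that "changes from baseline in laboratory values and vital signs that are not pre-specified as Tier 1 safety parameters will be considered Tier 3 safety parameters". Table 19 repeats this with its Tier 3 row "Change from Baseline Results (Labs, ECGs, Vital Signs)" and puts predefined limits of change in Tier 3 as well. Laboratory values at baseline and on treatment, and their change, are to be summarised by arm. No liver limit is defined anywhere in Section 8.

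On why the liver matters, Section 5.2.2.3 says: "However, certain AEs may be initially considered attributed to either study drugs, such as diarrhea, hypothyroidism, and liver enzyme elevation". Section 5.2.2.3.1 and Table 10 are devoted to ALT/AST elevation. Section 7.2.3.2 adds liver events of clinical interest (ECIs) for one arm: "The following events should also be reported as an ECI if they occur after the start of treatment in the axitinib/ pembrolizumab combination arm".

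Section 5.2.2.3.1 also reports the same event measured two ways in the first-line axitinib trial: "laboratory data showed that the rate of ALT elevation was 40.4% for all grade, 29.8% for Grade 1, 6.7% for Grade 2" and "reported ALT elevation regardless of causality was 10.6% for all grade, 4.8% for Grade 1, 2.6% for Grade 2, 3.2% for Grade 3".

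**The concern.** Secondary objective 3 is to evaluate and compare safety between arms. For the liver there is an objective measurement, collected in both arms and already in the chemistry panel (Table 14). The tier rule bypasses it for comparison and relies on whether an unblinded investigator entered an AE term.

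The incentive to enter that term is not the same in the two arms. An isolated ALT or AST above 5xULN is an ECI in the combination arm only. The fuller evaluation guideline for values above 3xULN is also written for that arm only. If reporting differs by arm, the published liver difference partly measures reporting. If reporting is equally incomplete in both arms, a real difference shrinks.

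Mean change from baseline would not fill the gap, because a small number of large elevations, cut short by dose interruption, hardly moves a mean.

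**Working it through.** **1. The plan's own figures.** In the axitinib trial (Section 5.2.2.3.1), the laboratory grades sum as 29.8 + 6.7 + 3.9 + 0 = 40.4%, and the AE grades as 4.8 + 2.6 + 3.2 + 0 = 10.6%. Both stated totals reproduce. In Phase 1b (Tables 2 and 3, N = 52), ALT is 18/52 = 34.6% by AE and 27/52 = 51.9% by laboratory, also as stated.

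**2. Restrict to the grades that matter.** Table 10 equates more than 3 to 5xULN with Grade 2 and more than 5xULN with Grade 3 or 4, so a threshold of more than 3xULN means Grade 2 or higher.

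| Source | Measure | Laboratory | AE term |
|---|---|---|---|
| Axitinib trial | ALT, all grades | 40.4% | 10.6% |
| Axitinib trial | ALT, Grade 2+ | 6.7 + 3.9 = 10.6% | 2.6 + 3.2 = 5.8% |
| Axitinib trial | ALT, Grade 3 | 3.9% | 3.2% |
| Phase 1b | ALT, Grade 2+ | 6 + 2 = 8/52 | 7 + 3 = 10/52 |
| Phase 1b | AST, Grade 3 | 0/52 | 3/52 |

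(The figure 10.6% occurs twice by coincidence: all-grade by AE and Grade 2+ by laboratory.) AE terms fall short of the laboratory count in one source and exceed it in the other.

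**3. Effect on a between-arm difference.** Inputs: about 430 per arm (861 randomized 1:1, Section 8.9) and an equal true laboratory Grade 2+ rate of 10.6%. The ratio of AE to laboratory rate in the axitinib trial is 5.8/10.6 = 55%. The sunitinib ratio is not given, so it is varied. AE rate = laboratory rate x reporting ratio, with the SAP's own Miettinen and Nurminen interval:

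- Reporting 100% in both arms: 46/430 vs 46/430, difference 0.0 (95% CI -4.2 to 4.2).
- Reporting 100% combination, 75% sunitinib: 46/430 vs 34/430, difference 2.8 (-1.1 to 6.8).
- Reporting 100% combination, 55% sunitinib: 46/430 vs 25/430, difference 4.9 (1.2 to 8.7).
- The reverse, 55% combination and 100% sunitinib: -4.9 (-8.7 to -1.2).

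The laboratory-based difference is 0 in every row.

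**4. Whether severe elevation gets an interval at all.** If the 5% rule is applied to a Grade 3-5 ALT term, an arm of 430 needs 22 subjects (5% of 430 = 21.5). The binomial chance of reaching that is 2% at a true 3.2% (axitinib trial, AE), 10% at 3.8% (Phase 1b, laboratory) and 76% at 5.8% (Phase 1b, AE).

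**5. Can laboratory data be compared fairly?** Scheduled chemistry comes from footnote u of flow charts 6.1 and 6.2. Combination: weeks 3, 6, 9, 12, 15 and 18. Sunitinib: weeks 4, 6, 10, 12, 16 and 18. That is 6 vs 6 draws through Week 18. Through Week 54 it is 54/3 = 18 vs 6 + (54 - 18)/6 = 12. The sunitinib draws at weeks 6, 12 and 18 follow two weeks off drug.

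**The case against.** A reader might infer from the all-grade figures that the plan builds in a large false excess. Taking a 51.9% laboratory rate in both arms, and AE-to-laboratory ratios of 18/27 = 67% for the combination and 10.6/40.4 = 26% for sunitinib, the AE difference would be 20.9 points (15.4 to 26.5). The documents do not support this. The 26% belongs to axitinib, which is in the experimental arm. The 67% is a ratio of two separate tables, not a capture rate, since Grade 3 AST shows AE cases that are not laboratory cases. The all-grade counts are mostly Grade 1 (19 of 27 in Phase 1b; 29.8 of 40.4 points in the axitinib trial). At Grade 3 the two ALT measures are close.

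The arms are also less unequal than they may look. The ECI for ALT/AST of at least 3xULN with bilirubin of at least 2xULN and ALP below 2xULN covers both arms. Table 11 has its own ALT/AST actions for sunitinib, and all AEs are reportable in both arms. Laboratory results do not go unreported: per-arm summaries and clinical review are planned, and Section 8.6.2 describes the Tier 2 intervals themselves as descriptive. The supplemental SAP is not available and could add a liver table.

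These points limit the size of the concern. They do not remove the gap, because Section 8.1 places the comprehensive plan in Sections 8.2 to 8.12, and there every between-arm liver interval comes from an AE term.

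**Conclusion.** The point holds as a gap in the safety analysis, not as a demonstrated reporting error. The tier rule leaves the between-arm liver estimate on an open-label reported term when an objective measure exists in both arms. The documents' own data show that the two measures can disagree in either direction.

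The size and direction of any error are unknown because sunitinib reporting is not given. At Grade 2 or higher the illustration runs from 0 with equal reporting to 4.9 points either way with 100% against 55%. It assumes an equal 10.6% laboratory rate, about 430 treated subjects per arm, and a ratio taken from a different trial and drug. Nothing here bears on the primary endpoints, power or alpha. Liver enzymes are one of three named overlapping examples, with diarrhea and hypothyroidism, not the only one.

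**What to change.** In Section 8.6.2 and Table 19, add as Tier 2, whatever the observed incidence, the percentage of subjects in each arm with:

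- ALT or AST >3xULN, >5xULN and >10xULN;
- ALT or AST >3xULN concurrent with total bilirubin >=2xULN.

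Compute these from laboratory data with the Miettinen and Nurminen 95% interval. The cut-points are already in Table 10 and Section 7.2.3.2.

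Base the main contrast on protocol-scheduled draws only, through Week 18 (6 per arm), and note that three of the six sunitinib draws follow the off-treatment period. Excluding unscheduled draws matters: Section 5.2.2.3.1 asks for a repeat within 24 to 72 hours and then twice-weekly tests after an elevation in the combination arm, which raises the chance of recording a higher peak there.

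Show all draws over all treatment as supportive, noting 18 vs 12 scheduled draws through Week 54 and the extra combination-arm tests. Do not use ECI counts as a between-arm measure.

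The cost is SAP wording and one table from data already collected. The downside is a few more unadjusted descriptive intervals. No clinical management rule changes.
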